9.2.5. Considerations for generalizability of study population

The results from the prospective registry, although limited to US participants, will likely be generalizable to the general population in the US and the EU for several reasons:

1. Participants in clinical research in the US are predominantly white, and racially/ethnically diverse groups are underrepresented, despite efforts by the industry and regulators to increase diversity.^{30,31} Pregnancy registries are not immune to this issue. As evidenced by several of the largest pregnancy registries conducted in the US and globally, the women who participate are predominantly white.³²⁻³⁴ The demographic characteristics of women who participate in clinical research in the US, and specifically pregnancy registries, align with those of the general EU population.

PFIZER CONFIDENTIAL

2. The demographic characteristics of patients with migraine in the US are similar to those in the EU. In the US and the EU, patients with migraine are predominantly white and female, and the disease tends to more frequently affect individuals aged 18 to 44 years.^{5,35} Gender-related differences are thought to stem from hormonal differences between males and females,³⁶ while race-related differences are thought to be attributable to differences in genetic vulnerability to migraine.³⁷

The US-based prospective registry collects detailed demographic data, including age, race, ethnicity, education, employment status, and income, as well as anthropometrics such as height, weight, and body mass index. These will be compared with those of women of child-bearing potential with migraine in the US, their source population, and in the EU to identify any issues with representativeness, if needed.

Based on the information provided above, it is expected that the data collected via this US-based study will be generalizable to the EU population. The representativeness of the data will be evaluated in each interim report by comparing the demographic and clinical characteristics of registry participants with those from the published literature on pregnant women with migraine, including results from the pan-European ConcePTION project on migraine.^{38,39}

9.3. Variables

9.3.1. Registry participant management and disposition

The following variables will be used to define inclusion in the main analysis population (defined in Section 9.7.1).

9.3.1.1. Valid versus invalid participants

A valid participant will be defined as a pregnant woman with sufficient data, submitted or confirmed by an HCP, for determining and meeting inclusion/exclusion into one of the study population cohorts. Participants who lack the minimum data required for determining inclusion or exclusion into one of the study cohorts or who lack confirmation from an HCP will be considered invalid. Participants who complete the *Weekly Log for Migraine Headaches and Acute Medications* and *Monthly Log for Preventive Migraine Medications*, documenting their exposure to acute and preventive migraine therapies during pregnancy will not be required to have HCP confirmation of exposure. Invalid participants will be enumerated in each registry report but will not be included in statistical analyses.

9.3.1.2. Prospectively enrolled versus retrospectively enrolled participants

The registry will encourage prospective registration; however, retrospective enrollment in the registry will be permitted. A prospectively enrolled participant will be defined as a pregnant woman who enrolls or makes initial contact with the registry prior to the pregnancy outcome. A retrospectively enrolled participant will be defined as a pregnant woman who enrolls in the registry after the pregnancy outcome has occurred. The registry will retrospectively enroll participants up to 12 months after the occurrence of their pregnancy outcome.

PFIZER CONFIDENTIAL

Retrospectively enrolled participants can be biased toward the reporting of more unusual and severe outcomes and are less likely to be representative of the general population than prospectively enrolled participants. Therefore, retrospectively enrolled participants will be excluded from the main analysis population (Section 9.7.1) but will be analyzed separately in supplementary analyses (Section 9.7.3.6).

Diagnostic prenatal tests (eg, ultrasound to scan for structural defects at approximately 20 gestational weeks, chorionic villus sampling, and amniocentesis) can determine with high accuracy whether a fetus has a structural or chromosomal abnormality. Therefore, inclusion of women who have had diagnostic prenatal testing prior to enrollment in the main analysis population may introduce bias. To examine this potential bias, a sensitivity analysis that applies a stricter definition of prospective enrollment will be conducted (Section 9.7.3.7). For this analysis, women who enroll in the registry prior to diagnostic prenatal testing will be considered prospectively enrolled, and women who enroll in the registry after diagnostic prenatal testing, regardless of the results, will be considered retrospectively enrolled. The outcomes of women who enroll prior to diagnostic prenatal testing will be compared with those of women who enrolled after diagnostic prenatal testing.

9.3.1.3. Exposure to excluded products

Women will be considered exposed to excluded products (other CGRP antagonists, CGRP monoclonal antibodies, and/or ditans) during pregnancy if a dose is taken at any time during pregnancy (from conception to pregnancy outcome) or prior to pregnancy (within a specified time based on the product's half-life). Participants will be considered exposed during pregnancy if a dose is taken prior to conception within a timeframe equivalent to 5 times the product's half-life.

Women who are exposed to excluded products during pregnancy and prior to study enrollment will not be permitted to enroll. Women who are enrolled but later exposed to excluded products (other CGRP antagonists, CGRP monoclonal antibodies, or ditans) will be excluded from the main analysis population (Section 9.7.1); however, these participants will be analyzed in supplementary analyses (Section 9.7.3.6).

9.3.1.4. Participants lost to follow-up

A participant will be considered lost to follow-up if follow-up information is never obtained or is unavailable after multiple attempts using various modes of communication; pregnant women without pregnancy outcome information will be considered lost to follow-up. Information from these participants (eg, baseline characteristics, abnormal prenatal test results, and reason for loss to followup, if available) will be summarized in each registry report, but these participants will be excluded from the main analysis population (Section 9.7.1). Live-born infants without follow-up data after birth will still have their pregnancy-related information included in the main analysis population.

PFIZER CONFIDENTIAL

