The registry will systematically collect information on major and minor structural malformations, transient malformations in term infants, and chromosomal defects that are apparent at birth and noted through infant age 1 year, including: congenital malformation(s) and details, if noted, type of congenital malformation(s) if applicable, attribution to drug therapy, and other factors that might have contributed to the outcome.

If a congenital malformation is reported, other data of interest can be collected through targeted followup.

PFIZER CONFIDENTIAL

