9.4.1.3. Information collected at pediatric follow-up

Timing of pediatric follow-up

If a live birth occurs, the mother will be asked to authorize the medical release for the infant's pediatric HCP to provide follow-up information. If authorization for medical release is obtained, the pediatric HCP will be asked to complete the *Infant Outcomes Form* at 4 and 12 months of age. At approximately 4 months after delivery, infant data at 2 and 4 months of age will be collected; at approximately 12 months after delivery, infant data at 6 and 12 months of age will be collected. To reduce recall bias, pediatric HCPs will be asked to provide data that are routinely documented in the infants' medical records at their visits at 2, 4, 6, and 12 months of age. This schedule follows the American Academy of Pediatrics' recommended infant well-child visit schedule.⁵²

Infant outcome information

Collected from pediatric HCP

- Date of follow-up evaluation
- Current age of infant
- Current weight, length, head circumference of infant
- Developmental milestones per the HCP's assessment of normal, delayed, etc.
- Congenital malformation(s) and potential contributing factors
- Infant death, including date and cause of death

Targeted follow-up after report of an event of interest

PFIZER CONFIDENTIAL

If there is a congenital malformation or other event of interest, additional information may be requested from the reporting HCP on the *Targeted Follow-up Form* to properly characterize the event.

Targeted follow-up information

Collected from HCP(s)—obstetric and/or pediatric

- Details of the congenital malformation or other event of interest
- Etiology
- Maternal infections/conditions of relevance to event
- Other information considered relevant by the HCP
- Specific questions requested by the birth defect evaluator (see Section 9.4.4)

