9.5.2. Full study

The full study will aim to prospectively enroll a minimum of 390 women with migraine who were exposed to rimegepant during pregnancy or just prior to pregnancy (up to 3 days prior to conception), as well as an internal comparison cohort consisting of 390 women with migraine who were not exposed to rimegepant during pregnancy or just prior to pregnancy (up to 5 product half-lives prior to conception). The target sample size for the registry is based on the primary outcome, MCM, which is also the outcome with the most restrictive denominators and 1 of the lowest prevalence rates in the general population. If all are evaluable for potential MCMs (evaluable being those for whom pregnancy outcome and major/minor congenital malformation assessments are obtained), and assuming an approximate 3% overall population prevalence of MCM, ⁵⁴ at α =0.05, this sample size provides 80% power to detect a 2.5-fold increased risk for overall MCM. Most registry power calculations are performed for overall MCM to detect an increased risk between 2- and less than 3-fold.⁵⁵ A midpoint threshold of a 2.5-fold increased risk was selected for this study. Assumptions for study calculations are consistent with those applied in the retrospective pregnancy outcomes study (NDA 212728, postmarketing requirement 3799-7, Pfizer study C4951006 [formerly BHV3000-403]).

Prospective enrollment can occur only after pregnancy is recognized but while the pregnancy is ongoing. Therefore, early pregnancy losses will not be captured, and a live birth rate higher than that of the general population would be expected. Research shows that approximately 90% of pregnancies enrolled in pregnancy exposure registries result in a live birth.^{56,57} Assuming that 90% of prospectively enrolled pregnancies result in live births and 10% are lost to follow-up,⁵⁸ at α =0.05, the study sample of 390 prospectively enrolled pregnant women in each internal cohort would result in 316 evaluable participants per cohort. Therefore, the study would have 80% power to detect a 2.7-fold increased risk of overall MCM (Table 2).

PFIZER CONFIDENTIAL

Outcome	N per cohort	Reference rate	Relative risk detectable	Power ^b
МСМ	390	3% ^{54,55,59}	2.5	80.6%
МСМ	316 ^a	3% ^{54,55,59}	2.7	80%

Table 2.	Sample Size and Power Estimates for Primary	Outcome, MCM

MCM = major congenital malformation; reference rate = prevalence rate of outcome in general population for pregnant women of any age

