9.7.3.3. Calculation of outcome prevalence

Prevalence rates of the outcomes of interest will be calculated according to the conventions described in Table 4. In general, the prevalence of each outcome will be calculated by dividing the number of cases of the outcome by the appropriate denominator for that particular outcome, based on clinical knowledge and/or the methodology used by the external comparator. Prevalence is preferred over incidence when examining pregnancy outcomes, such as congenital malformations, because incidence cannot be reliably estimated given the complexities in the reproductive process.⁶⁷

For most outcomes, the main analysis population (denominator) will be the number of pregnant women with pregnancy outcome data, the number of live births, or the number of infants with follow-up data at the timepoint of interest, as appropriate; however, for some outcomes, the main analysis population (denominator) will be restricted based on certain relevant factors:

- For MCM, prevalence in the rimegepant-exposed cohort will be calculated among the subset of women who are exposed during the first trimester.
- For MCM, prevalence will be calculated among live births for the primary analysis, and a secondary analysis will be conducted among live births and fetal losses.
- For preterm birth, SGA, and postnatal growth deficiency, prevalence will be calculated among singleton live births due to the higher risk of these outcomes in twins and higher-order multiples.
- For live birth and infant outcomes (ie, preterm birth, SGA, postnatal growth deficiency, and infant developmental delay), prevalence will be calculated among live births/infants without MCMs.
- For postnatal growth deficiency, infants born preterm or SGA will be excluded from the main analysis population (denominator).
- For infant developmental delay, infants born preterm will be excluded from the main analysis population (denominator).
- For SAB and preterm birth, prevalence will be calculated among the subset of women who are enrolled in the registry prior to 20 and 37 gestational weeks, respectively.
- For some outcomes, prevalence will be calculated at multiple timepoints. For example, postnatal growth deficiency and infant developmental delay will be assessed at 2, 4, 6, and 12 months of

PFIZER CONFIDENTIAL

infant age. At each timepoint, prevalence will be calculated among infants with data available for the particular outcome at that timepoint.

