For comparison with external comparators, the prevalence rates of the outcomes of interest among the rimegepant-exposed participants of the main analysis population will be calculated according to the conventions used by the selected external comparators. For example, for the comparison with MACDP, live births and stillbirths with MCMs (including MCMs not associated with medication exposure) will be included in the numerator, and the denominator will be the number of live births. The MACDP calculates rates by this convention, which increases sensitivity. Likewise, for comparisons with the external cohort of pregnant women without migraine (from the retrospective pregnancy outcomes study), the conventions used to calculate outcome prevalence rates in the internal and external cohort will be aligned.

In addition, "crude" prevalence rates, without limitations and exclusions, may be conducted to avoid restricting the main analysis population (denominator). For example, infants with MCM and/or infants born preterm may be included for the prevalence rate calculation of infant developmental delay.

Outcome	Numerator	Denominator	
Primary Outcome – MCM			
Primary analysis: among live births with 1 st trimester exposure (if applicable for cohort)	Live births with confirmed MCMs (excluding MCMs not associated with medication exposure) among women with pregnancy outcome data and exposure during 1 st trimester (if applicable)	Live births among women with pregnancy outcome data and, if applicable, exposure during 1 st trimester	
Secondary analysis: among all pregnancy outcomes with 1 st trimester exposure (if applicable for cohort)	Live births and fetal losses with confirmed MCMs (excluding MCMs not associated with medication exposure) among women with pregnancy outcome data and, if applicable, exposure during 1 st trimester	Live births and fetal losses among women with pregnancy outcome data and, if applicable, exposure during 1 st trimester	
Secondary analysis: among live births with exposure at any time during pregnancy (if applicable for cohort)	Live births with confirmed MCMs (excluding MCMs not associated with medication exposure) among women with pregnancy outcome data and, if applicable, exposure at any time during pregnancy	Live births among women with pregnancy outcome data and, if applicable, exposure at any time during pregnancy	

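### The primary MCM denominator does not require a malformation assessment and Table 4 sets no detection age, so unequal infant follow-up between cohorts would bias the relative risk, probably modestly.

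*Protocol*

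**What the plan says.** **Detection window.** Section 9.3.4.1 collects malformations "that are apparent at birth and noted through infant age 1 year". The Pregnancy Outcome Form records them at birth (Section 9.4.1.2), and the Infant Outcomes Form records them from the visits at 2, 4, 6 and 12 months.

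**Infant follow-up is conditional.** Section 9.4.1.3 says: "If authorization for medical release is obtained, the pediatric HCP will be asked to complete the" Infant Outcomes Form.

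**Who stays in.** Section 9.3.1.4 excludes pregnancies without an outcome as lost to follow-up, but adds: "Live-born infants without follow-up data after birth will still have their pregnancy-related information included in the main analysis population".

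**Primary measure.** Section 9.7.3.3 says: "For MCM, prevalence will be calculated among live births for the primary analysis". In Table 4 the primary numerator is "Live births with confirmed MCMs (excluding MCMs not associated with medication exposure) among women with pregnancy outcome data and exposure during" the first trimester (if applicable). The denominator is "Live births among women with pregnancy outcome data and, if applicable, exposure during" the first trimester. Neither names an age of detection.

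**Evaluable.** Section 9.5.2 rests the sample size on a narrower group, "evaluable being those for whom pregnancy outcome and major/minor congenital malformation assessments are obtained".

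**Checks on loss.** Section 9.9 compares the proportion lost to follow-up between cohorts for pregnancies only. Section 9.7.3.7 lists three sensitivity analyses, none of which concerns infant follow-up, and leaves missing-data analyses optional.

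**The concern.** Under Table 4 an infant with no paediatric data counts in full in the denominator, but can enter the numerator only if the MCM was seen before birth or at birth. The effective detection window is then close to zero for some infants and 12 months for others. The primary relative risk mixes the risk of malformation with the completeness of infant follow-up.

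The protocol treats comparable outcomes differently. Postnatal growth deficiency and developmental delay are calculated only among infants with data at the time point (Section 9.7.3.3). The primary outcome, collected over the same 12 months, has no such rule.

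The costlier error in a safety study is attenuation, which occurs if exposed infants are followed less completely than comparators. The study is sized only for a 2.5- to 2.7-fold risk, so it has little room for that.

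**Working it through.** **1. The plan's own figures.** Two-sided normal approximation, alpha 0.05, equal cohorts, reference rate 3% (Section 9.5.2, Table 2):
- 390 per cohort, 3% vs 7.5% (RR 2.5): power 80.6%, as stated.
- 390 × 0.9 × 0.9 = 315.9, so 316. At 3% vs 8.1% (RR 2.7): power 80.1%, stated as 80%.

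The arithmetic is right. The 316 removes pregnancies without a live birth and losses to follow-up. It removes nothing for a missing malformation assessment, so numerically it matches the Table 4 denominator rather than the evaluable definition beside it.

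**2. Bias formula.** Let b be the share of 12-month MCMs found at birth, and f1 and f0 the shares of exposed and comparator live births with infant follow-up. Assume follow-up is unrelated to MCM status and b is the same in both cohorts. With all live births in the denominator:

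RR observed / RR true = (b + (1 − b) f1) / (b + (1 − b) f0)

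**3. Results.** The protocol gives neither b nor f, so all of these are assumptions.

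| f1 vs f0 | b = 0.5 | b = 0.67 | b = 0.8 | b = 0.9 |
|---|---|---|---|---|
| 90% vs 70% | 0.95/0.85 = 1.12 | 1.07 | 1.04 | 0.99/0.97 = 1.02 |
| 70% vs 90% | 0.89 | 0.93 | 0.96 | 0.98 |
| 95% vs 60% | 0.975/0.80 = 1.22 | 1.13 | 1.08 | 1.04 |
| 60% vs 95% | 0.82 | 0.88 | 0.93 | 0.97 |
| Equal | 1.00 | 1.00 | 1.00 | 1.00 |

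**4. Effect on power** (316 per cohort, true RR 2.7, planned 80.1%):
- 70% exposed vs 90% comparator: observed RR 2.42 (b = 0.5) to 2.65 (b = 0.9); power 65.5% to 77.6%.
- 90% in both cohorts: no bias; power 77.9% to 79.7%, because fewer MCMs are detected.

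**5. Scale against sampling error.** At 316 per cohort, 316 × 0.03 = 9.5 comparator MCMs are expected. At RR 2.5 there are 23.7 exposed. The standard error of log RR is √(1/23.7 + 1/9.48 − 2/316) = 0.376, so the 95% interval spans a factor of exp(1.96 × 0.376) = 2.1 each way, about 1.2 to 5.2.

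**6. Two tempting remedies.**
- *Restrict to infants followed to 12 months.* At 90%, 80% and 70% follow-up in both cohorts, 284, 253 and 221 per cohort remain, with power at RR 2.7 of 75.8%, 70.8% and 65.0%.
- *Keep infants diagnosed early but drop unaffected infants without 12-month data.* Prevalence becomes p(b + (1 − b)f) / (f + pb(1 − f)). Take p = 3% in both cohorts. With b = 0.7, f = 0.9 gives 0.0291/0.9021 = 3.2% and f = 0.7 gives 0.0273/0.7063 = 3.9%, a ratio of 0.83 although the true RR is 1. With b = 0.5 and f of 0.9 vs 0.6 the ratio is 0.0285/0.9015 over 0.024/0.606 = 0.80. The Table 4 rule gives 1.07 and 1.19 on the same inputs, so this remedy is no better.

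**The case against.** Much of the plan works against the problem, and these points stand:
- Births never assessed for malformations should be few. The obstetric provider reports malformations on the Pregnancy Outcome Form (Section 9.4.1.2). Missing critical data prompt three further attempts (Section 9.4.2). The mother supplies the outcome only as a fallback (Section 9.4.4).
- Permission to contact the infant's provider is an inclusion criterion (Section 9.2.1), and participant compensation for live births follows the 12-month data (Section 9.2.4.2).
- Section 9.7 already summarises infant outcome information by cohort, with the amount missing for each data point, so follow-up completeness will be visible.
- Nothing shows that follow-up will differ between cohorts.

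A reader might infer more than the documents support:
- *That the protocol declares unfollowed infants free of MCM.* Section 9.3.1.4 speaks only of pregnancy-related information. The effect follows from Table 4.
- *That the exposed prevalence is understated against external comparators.* This depends on each comparator's own detection window, which the documents do not give. Section 9.7.3.3 commits to following each comparator's conventions.
- *That a large bias is to be expected.* A factor of 1.19, or 0.84 reversed (a true 2.5 read as 2.1), needs half of MCMs found after birth and a 30-point gap (0.95/0.80).

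Leaving the matter to the SAP is only a partial answer. Table 4 itself fixes the denominator, and Section 9.7 requires a protocol amendment for major changes to the primary outcome definitions or their analyses.

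**Conclusion.** The concern holds in a limited form. Table 4 omits the assessment condition that Section 9.5.2 uses and sets no detection age. Unequal paediatric follow-up would therefore bias the primary relative risk, and none of the listed sensitivity analyses would show it. The main route is MCMs recognised after birth, not births that were never assessed.

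The direction is unknown and the size modest: a factor of about 0.89 to 1.12 for a 20-point gap with 50% to 90% of MCMs found at birth, and none if follow-up is equal. Both inputs are assumed. This is well inside the sampling error of the estimate, but it is systematic and cheap to address. The stated power is not in error.

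**What to change.** 1. In Table 4, limit the MCM denominators (and the matching numerators) to live births with a malformation assessment obtained, as in Section 9.5.2. Judge this by whether the assessment was completed, not by its finding. State the detection window as birth to 12 months.
2. In Section 9.7.3.7, add a prespecified sensitivity analysis that counts only MCMs identified by the birth assessment on the Pregnancy Outcome Form, so that detection time is the same in both cohorts. It should not replace the primary analysis: expected comparator MCMs would fall from 9.5 to between 4.7 (9.48 × 0.5) and 8.5 (9.48 × 0.9).
3. In Section 9.9, extend the comparison of differential loss to infants without paediatric follow-up.
4. For any 12-month estimate, treat incomplete follow-up alike for cases and non-cases, for example by cumulative risk with censoring at last infant contact or by weighting for follow-up. Do not keep early cases while dropping unfollowed, unaffected infants.

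Cost: wording in three sections, one extra analysis, and a few unassessed births leaving the denominator. No new data are needed, and comparative analyses are run only at the end of the study.
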